Outcomes: We will estimate the total cost and average cost per person in treatment, and the cost per person successfully retained in HIV care at 12 months for both the Coach Mpilo and the standard of care study arms. Additional outcomes will include the intermediary cost-effectiveness outcomes of incremental cost per additional participant retained, and long-term cost-effectiveness outcomes from modelling work will include incremental cost per life year saved and incremental cost per HIV infection averted.

Expected outcomes: Our findings will add to the limited evidence on the cost-effectiveness of peer-led interventions for people living with HIV. They will also indicate the role of peer-led interventions in closing the gender gap in ART coverage and viral suppression rates. Finally, they will be directly useful for decisions about whether to allocate scarce resources to Coach Mpilo, or whether the use of the intervention should be more narrowly targeted to specific population segments.

Aim 4: Assess the acceptability, feasibility and fidelity of the Coach Mpilo program

To inform intervention refinements and policy decisions on the scale-up of Coach Mpilo and peer-led interventions more generally, we will quantitatively and qualitatively assess implementation outcomes alongside effectiveness and cost-effectiveness of the intervention. Implementation outcomes are viewed as important for evaluation of complex health interventions in research and practice,¹⁶ providing indications into the implementation process as preconditions for attaining intended intervention engagement and health outcomes.¹⁷ Table 2 outlines implementation outcome-specific conceptual and definitional distinctions as well as proposed methods to measure these outcomes.

We will use Sekhon's 2017 Theoretical Framework for Acceptability (TFA)¹⁸ to assess the feasibility and acceptability of the intervention, informing interpretation of effectiveness overall (Aim 1), for sub-groups (Aim 2), and cost-effectiveness (Aim 3) by describing how acceptable the intervention is and how feasible the intervention is to deliver, from different stakeholder perspectives, and by describing the fidelity of the intervention.

Table 2. Aim 4 Qualitative and quantitative implementation science methods: conceptual and theoretical distinctions

Implementation outcome	Intervention stakeholder	Measures	Analysis
Acceptability ^{17,18} "The perception among implementation stakeholders that a given treatment, service, practice, or innovation is agreeable, palatable, or satisfactory"	Participants	Baseline survey - prospective acceptability, assessing values alignment and ethicality	Descriptive analysis
	Coaches	Follow-up survey - retrospective acceptability, using AIM and CSQ-8, coach uptake and retention in the coach program Participant IDIs Coach IDIs	Deductive and inductive thematic analysis

Implementation outcome	Intervention stakeholder	Measures	Analysis
Feasibility¹⁷ “The extent to which a new treatment, or an innovation, can be successfully used or carried out within a given agency or setting.”	Participants Coaches Squad managers	Participant IDIs Coach IDIs Coach logs Coach-to-Coach Whatsapp group Adaptation logs	Descriptive analysis Deductive and inductive thematic analysis
Fidelity¹⁷ “The extent to which the intervention is delivered as intended”	Participants Coaches Squad managers	Participant IDIs Coach IDIs Coach logs Coach-to-Coach Whatsapp group Debriefing Adaptation logs	Deductive and inductive thematic analysis

Participants: Aim 4 will be conducted with quantitative and qualitative data collected from trial participants (Aim 1 and 2) coaches (Aim 2) and from the Squad Manager.

Procedures and data collection: We will collect both i) primary quantitative survey data at baseline and six month follow-up (through Aim 1 survey instruments); ii) primary qualitative data from intervention arm participants that decline a coach, participants who are supported by a coach at six-month follow up, and coaches immediately after the intervention stops being implemented (through Aim 2 IDI instruments); iii) routine administrative data during intervention preparation and implementation. Sampling, consenting process and data collection procedures for primary data are described in Aim 1 and 2. **Quantitative:** At baseline, we will assess participants’ affective attitude and values alignment to understand prospective acceptability. In the follow up survey with intervention arm participants, we will use the Acceptability of Intervention Measure (AIM)¹⁹, and the Client Satisfaction Questionnaire (CSQ-8).^{20,21} AIM and CSQ are widely used instruments with published data on reliability and validity.²¹ Results from the AIM and CSQ-8 can be compared with intervention feedback from IDIs with participants. In addition, data from the baseline survey will be used to assess potential determinants of intervention acceptability (AIM and CSQ-8) measured in the 6 month follow-up study. Consenting process and data management procedures will follow those laid out in Aim 1. **Qualitative:** **Follow-up in-depth-interviews** described in Aim 2 include topics which answer our implementation research questions, focusing on retrospective acceptability (the semi-structured IDI guide is found in Appendices D and E). **Coach log:** an existing routine administrative data collection tool has been adapted to focus on implementation choices, their determinants, and

coach-participant relationship quality. **Adaptation log:** an existing routine administrative data tool on implementation adaptations and their determinants will be used, completed by Squad Managers who hold regular meetings with individual coaches and collectively with the entire coach cohort. **Coach-to-Coach WhatsApp Group:** the implementing partner routinely establishes a WhatsApp group used by Coaches and the Squad Manager (i.e. not including any clients/participants). Data from this group will include challenges Coaches are facing and solutions suggested by other coaches. Coach phone numbers and any other identifying information derived from these communications will be treated as confidential, stored securely, and handled in accordance with the study's data management plan. **Training observations:** an existing routine administrative data tool will be used to collect semi-structured observations at the initial coach training and at a refresher training after two months of implementation. **Monthly and quarterly implementation reports and follow-up discussions:** these reports will be developed by Population Services International and Matchboxology, providing both quantitative data on reach and their own observations on fidelity, reach, mechanisms of change and implementation strategies and determinants. Monthly reports will be accompanied with a follow-up discussion conducted in English, transcribed through AI transcriptions.

Analysis: Quantitative analysis. Among Aim 1 intervention group participants, we will conduct descriptive analysis of data from the AIM and CSQ-8 scales and linear regression analysis to assess what factors at baseline were associated with these scales. Qualitative data analysis. We will conduct ongoing saturation analyses, based on iterative coding during data collection. Transcriptions will be checked for accuracy and uploaded into Dedoose qualitative analysis software. We will also enter all observational notes as memos. Data analysis will be iterative, and include both deductive and inductive approaches to thematic analysis. Deductive analysis will engage topics from our instruments in interpreting and organising data and we will use the Theoretical Domains Framework (TDF) for mapping and reporting implementation-related themes. The TDF is used extensively in implementation science, and is valuable in identifying barriers and facilitators to intervention implementation across 14 domains relevant to behaviour change.²² To ensure accurate interpretation, we will conduct independent reviews of transcripts to contribute to the study's overarching thematic framework for data interpretation. The investigators will compare frameworks for consistency and discrepancies. Data will be re-examined, allowing for discussion and making interconnections between research questions, coding categories, and raw data. Data integration: Analysis of data from this multi-method aim will require integration of multiple data sources. We will follow a triangulation protocol, ensuring systematic integration of data analysis, examining and responding to completeness, convergence, dissonance and silence across findings.^{23–25} Qualitative findings will be compared with quantitative findings from descriptive analysis, aiming to identify inferences or draw conclusions at the point of interpretation, and at the point of reporting in a synthesis or discussion section of our publications.²⁶

Expected outcomes. Findings from Aim 4 will advance our understanding of how the Coach Mpilo intervention is adopted, delivered, adapted and sustained in this new study setting and context. Evaluating feasibility, acceptability and fidelity will improve our ability to interpret whether results reflect the effectiveness of the Coach Mpilo intervention itself as well as whether

and how changes in delivery influence these outcomes, to guide improvements, scale-up, and policy decisions.

Quality assurance: We will monitor depth of discussions and observational memos through immediate review of interview materials, and if necessary, refine probes and guidance in our instruments, and conduct additional interviewer and/or observer training.

ETHICAL CONSIDERATIONS

Ethical review

This study will be conducted in compliance with the protocol, applicable regulatory requirements (including POPIA), and ethical guidelines for research with human subjects in South Africa. Ethical oversight will be provided by the University of the Witwatersrand HREC (Medical), University of Cape Town HREC, and University of Pennsylvania IRB.

The protocol, information sheets, other requested documents, and any subsequent modifications will be reviewed and approved by the University of Witwatersrand, University of Cape Town, and University of Pennsylvania institutional review boards (IRBs) prior to starting this study. Subsequent to initial review and approval, the study team will submit progress reports as requested or required by the various IRBs.

All study staff will be trained in human subject's protection and study procedures to ensure that they understand both research confidentiality requirements and study confidentiality procedures.

Informed consent

Written informed consent will be required from all participants. As part of the informed consent process, potential participants will be given two copies of the Informed Consent Form, and a trained interviewer will review this document with them. It will contain: (1) the purpose and methods of the study, (2) alternatives to participation in the study, (3) procedures to protect confidentiality, (4) their rights to withdraw from the study at any time, (5) the fact that their non-participation will not have adverse effects, and (5) persons to contact if they have any questions about the study.

After reviewing the information, the study interviewer will ask follow-up questions to ensure that the informed consent process has been well understood by the potential participant and then ask her to sign the study copy of the written informed consent form (Appendix A). The signed copy will be retained for the study records, and the participant will be allowed to take the other copy, which can also be signed if they choose. In addition, a separate written informed consent process is in place for participants taking part in the in-depth interviews, which includes explicit consent for audio recording. The corresponding consent form is provided in Appendix H.

Study benefits

By taking part in this study, participants will not receive any direct benefits, aside from what is outlined in the study compensation section below. However, participation in this research could benefit the community as a whole. In this research we will evaluate an intervention to improve reengagement and retention in HIV care, which may in turn increase the health and well-being of people living with HIV and their families. This study will also potentially advance the science of peer-led programmes to improve health outcomes (HIV-related and beyond [e.g. Tuberculosis]).

Risks

This study poses low risk to participants. Participants will be offered the support of a Coach for 6-months. An information sheet provided to participants will make it clear that accepting or not accepting the offer of a Coach will in no way impact the care they receive in the public or private health care system. See Appendix A for an example of the information sheet on Coach Mpilo that participants will be provided.

There is always the possibility of a breach of confidentiality when conducting research. While this is acknowledged, there is very low likelihood because of the precautions that will be taken to protect confidentiality. If, however, confidentiality was breached it is possible that the data on the participant's HIV status and sexual history becomes public. For the participant this may result in stigmatisation and discrimination. To ensure participants confidentiality we will (1) ensure that the only study document that will contain an identifier is the written informed consent form, and this will be kept separate from other study data; (2) all data will be kept strictly confidential. All data files will be stored on password protected servers and devices that meet the requirements of local and international IRBs for secure data storage.

Participants have the option to withdraw from the study at any point should they feel uncomfortable or no longer be interested or willing to continue.

Study compensation

Participants will be reimbursed for their time and travel costs at minimum ZAR250 (~USD14.80) in grocery vouchers for study participation or in person visits. These grocery vouchers will be generated electronically and shared with the participant using only their cellphone number. This amount fairly compensates participants for their time and convenience; participants will not incur any study-related travel costs.

Safety and adverse events

There is the possibility that questions in the baseline survey asked to assess mental health may either give rise to some discomfort among participants or result in participants disclosing acute problems being experienced by themselves. To minimise risk and support participants should a case arise, study staff will be carefully trained on the standard operating procedure (SOP) for assessing and managing psychological risk. This is found in Appendix G. In addition, a referral form is available to facilitate appropriate psychosocial support for participants who request or

are identified as needing additional assistance (See Appendix I). Besides this risk, there are no other known safety or adverse events anticipated for participation in this study.

Privacy and confidentiality

The surveys will be conducted on handheld devices using survey software SurveyCTO and the SurveyCTO Collect application hosted by the University of Cape Town server. The devices will be encrypted and password protected so that, in the event of theft or loss, the information stored on these devices will not be accessible. Raw data will be loaded onto a secure SurveyCTO server via the cellular network. The data will be encrypted and only accessible by the research team. This study ensures all parties adhere to the Protection of Personal Information Act (POPIA). The data collected will be anonymous and a study ID will be assigned to participants.

Confidentiality measures will apply to all aspects of the study process from the time of first engaging with a participant at recruitment through to the data collection procedures. All study-related information will be stored securely. All paper-based participant information that includes any personal identifying information will be stored in locked file cabinets in areas with access control. Forms will be identified by a unique identification number to maintain participant confidentiality. All electronic databases will be secured with password-protected access systems. All folders will be encrypted using Cryptomator. Identifiers will be separated from the data that will be used for analysis and a key will be stored separate from the files for analysis. This key will be retained until the study results are finalized, at which point it will be destroyed. Participant study information will not be released without their written permission, except as necessary for monitoring by funders or local government authorities.

Study administration and data management

Study implementation will be directed by this protocol as well as study-specific procedures. Standard operating procedures will outline more detailed procedures for conducting this study. Regular meetings/teleconferences with investigators will occur to review study progress with corrective feedback supplied as necessary to implement the protocol.

This study ensures all parties adhere to the Protection of Private Information Act (POPIA). The study databases resulting from data collection will not contain identifying information and will be organised by assigned unique identifiers. All database files will also be password-protected, and only study staff will have access to the files. The study team based in South Africa and those outside of South Africa will be given access to the de-identified data through a Secure File Transfer Protocol (SFTP) link. All data will be managed by J-PAL's data management system.

All data will be captured and stored electronically through SurveyCTO which holds high data security features necessary for academic research. The electronic study records will be kept for ten years after study completion before destroying them.

Study monitoring

The study will be monitored by investigators and study managers from J-PAL, with additional support provided by collaborators from the University of Pennsylvania, and The University of The Witwatersrand. The study sponsor, The Fund for Innovation in Development (FID) will conduct auditing of study activities on an annual basis to ensure the scientific integrity of the study and to ensure the rights and protection of study participants. Monitoring and auditing activities may be conducted by:

- Staff ("internal")
- Authorised representatives of the University of Pennsylvania, University of Cape Town and The University of The Witwatersrand

Participants will complete the study survey on SurveyCTO, which is an online database. There will be no paper based records. All data will be captured and stored electronically on SurveyCTO which holds high data security features necessary for academic research. The electronic study records will be kept for ten years after study completion before destroying them.

Vulnerable populations

We will enroll men living with HIV of consenting age (18 years and older). Participation will occur with full informed consent, confidentiality safeguards, and in collaboration with trusted community and health partners to minimize potential risk and ensure respect for participants' dignity and autonomy.

Participant withdrawal

Participants can withdraw from the study at any point should they feel uncomfortable or no longer be interested or willing to continue.

References

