Inclusion criteria: Men living with HIV must meet the following criteria: (a) aged ≥ 18 years; (b) previously receiving HIV care at the study clinic; (c) missed their most recent ART clinic appointment by >28 days, (d) not planning to relocate to another region within the next 12 months; (e) able and willing to provide informed consent; (f) not currently taking ART. Importantly, agreement to be contacted by a coach (if selected) is not an eligibility criterion as our goal is to obtain generalizable evidence of the overall effectiveness of the Coach Mpilo program (uptake of communication with coaches will be explored in Aim 2).

Consenting process: Study staff will review the informed consent form with men who meet the inclusion criteria and answer any questions that men may have about study participation. The consent form (see Appendix A) includes a brief description of the Coach Mpilo intervention and the goals of the study. Staff will also obtain consent to review clinic records for participants. Those who provide informed consent and meet criteria for enrollment will proceed to randomization.

Data collection

Baseline survey: Study staff will administer a baseline questionnaire to obtain information on, among other things, participants' demographic characteristics, socio-economic status, health behaviour (HIV testing history, sexual behaviour, alcohol use), future outlook, internalized stigma and mental health. The baseline survey is found in Appendix B.

Follow-up survey: Study staff will contact participants at six months and administer an in-person

follow-up survey; many of the questions administered at baseline will be assessed again. The follow-up survey is found in Appendix C.

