Clinic records: We will obtain participants' health outcome data from electronic clinic data via TIER.Net (South Africa's national electronic HIV/TB monitoring system), to assess individual- and facility-level outcomes related to HIV. Where necessary for confirmation we will also retrieve data from physical clinic files. With consent from participants, we will use the participants folder number to match to their Tier.Net data at the clinic or subdistrict level. In cases of missing, mismatched, or duplicate folder numbers, fallback matching strategies may be applied using combination variables such as names, mobile phone number, year of birth, and only within data security constraints. We will conduct periodic validation and deduplication processes to improve linkage accuracy and reduce error. In addition, participants' data on laboratory tests relevant for HIV care (including viral load tests) will be requested from the National Health Laboratory Services (NHLS). All data will be handled in accordance with ethics approvals and national data protection standards. The study team will report linkage rates and assess potential bias due to non-linkage in the final analysis.

Coach Log Book: To collect data on the engagement between coaches and their clients, the coaches will maintain a log book of the dates, duration and mode (e.g., in-person, telephone call, WhatsApp messages) of contact with clients.

Randomization: Following the baseline survey, participants will be randomized (1:1) to a control group that receives the SOC and an intervention group that receives SOC plus the Coach Mpilo intervention. For the SOC, participants will receive the standard in-person tracking and tracing support as per the South African National Guidelines for individuals living with HIV who have missed clinic appointments. For the intervention group, participants will be informed about the potential support from a Coach. They will be provided with the details of their assigned coach and contact details for them to reach out to the Coach. In addition, permission will be obtained to provide their contact details to the Coach so that the Coach can initiate contact with them.

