Outcomes: The primary outcome will be retention in HIV care at 12 months, defined as attending a follow-up clinic visit on or before 12 months and obtaining adequate ART refills for a supply of medications at 12 months post study enrolment. Studying this outcome will address an important question about whether time-limited, resource-intensive interventions like Coach Mpilo have a durable effect on participants' health outcomes. The outcome also features prominently in cost-effectiveness modeling that we will undertake.

Secondary outcomes will include retention in care at 6 months; viral suppression (<50 copies/ml) at 6 and 12 months; and adherence over 6 and 12 months using proportion of days covered (PDC). In addition, we will examine outcomes measured in the 6-month follow-up survey: HIV-status disclosure, mental health, internalized stigma, self-esteem, employment and social isolation.

Analyses: Primary analysis: We will conduct intention-to-treat analysis and estimate a logistic regression model that includes clinic fixed effects and month of enrollment, and controls for baseline participant characteristics that are significantly different between study groups.

Secondary analyses: We will repeat the primary analyses for each secondary outcome. Analysis of six-month outcomes will indicate whether Coach Mpilo has promising immediate effects on participants' health and well-being. Analyses of outcomes such as mental health, social isolation, and future orientation will provide insights on potential mechanisms by which the Coach Mpilo intervention may affect men's health.

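### Primary retention is read from clinic- or subdistrict-level TIER.Net records with no rule for care at another facility, so ART resumed outside the linked area may be missed, by an unknown amount in each arm

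*Protocol*

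**What the plan says.** Protocol, Data collection, Clinic records: "We will obtain participants' health outcome data from electronic clinic data via TIER.Net". The folder number is used to "match to their Tier.Net data at the clinic or subdistrict level"; which of the two levels applies is left open. Three supports are named:

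- "In cases of missing, mismatched, or duplicate folder numbers, fallback matching strategies may be applied", using names, mobile number and year of birth.
- "Where necessary for confirmation we will also retrieve data from physical clinic files".
- "The study team will report linkage rates and assess potential bias due to non-linkage in the final analysis".

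The same paragraph says that HIV laboratory results, including viral load, will be requested from the national laboratory service (NHLS). It does not say whether they play any part in the retention outcome.

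Protocol, Aim 1, Outcomes: primary retention means "attending a follow-up clinic visit on or before 12 months and obtaining adequate ART refills" to have a supply at 12 months. No facility is named, and nothing is said about a man whose refills are recorded somewhere else.

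Protocol, Inclusion criteria: men must be "not planning to relocate to another region within the next 12 months".

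**The concern.** The outcome is meant to be retention in HIV care, but the named source sees only care inside the area that is linked. Every participant has already dropped out of care at the study clinic, and the setting is a dense metropolitan area in which another facility may be within reach. Some men may therefore restart ART somewhere the linked records do not cover. Their old record still matches and shows no recent visit or refill, so in a two-category outcome they look disengaged.

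If the same share is missed in both arms, the risk difference shrinks. If the share differs by arm, the primary comparison is biased, upward or downward. The retention result also feeds the cost per person retained and the modelled ART interruption rates in Aim 3, where care at another facility is not an interruption.

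**Working it through.** **Inputs from the protocol (Sample size and power calculations; Randomization).** Control retention 50% (range 40-60%), difference 10 points, 80% power at N = 786, target about 800, allocation 1:1. Alpha is not stated in that section; two-sided 0.05 is assumed here.

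**Step 1: the plan's own figure.** With variance 0.25 in both arms, n per arm = 2 × 0.25 × (1.960 + 0.842)² / 0.10² = 392.4, rounded up to 393, so 786 in total. The pooled two-proportion formula gives 388 per arm, or 776. At 400 per arm, power for 50% vs 60% is 81.3%. The design figure reproduces, so the point does not rest on an error there.

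**Step 2: model for missed care.** Let m be the share of truly retained men whose care lies outside the linked records. Recorded retention = true retention × (1 − m). The protocol gives no value for m; every value below is an assumption.

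**Step 3: equal m in both arms, true 50% vs 60%, 400 per arm.** Recorded difference = 0.10 × (1 − m).

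| m | Recorded retention | Difference | Power |
|---|---|---|---|
| 0% | 50.0% vs 60.0% | 10.0 points | 81% |
| 5% | 47.5% vs 57.0% | 9.5 points | 77% |
| 10% | 45.0% vs 54.0% | 9.0 points | 72% |
| 15% | 42.5% vs 51.0% | 8.5 points | 67% |

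**Step 4: unequal m.**

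- Control 10%, coach 5%, true 10 points: 0.60 × 0.95 − 0.50 × 0.90 = 0.570 − 0.450 = 12.0 points.
- Control 5%, coach 10%, true 10 points: 0.60 × 0.90 − 0.50 × 0.95 = 0.540 − 0.475 = 6.5 points; power 45%.
- Control 10%, coach 5%, no true effect (50% in both arms): 0.50 × 0.95 − 0.50 × 0.90 = 2.5 points; the test rejects 10.9% of the time at a nominal 5%.

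**Step 5: do the stated safeguards catch these men?**

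- Non-linkage assessment: it addresses participants who cannot be matched. A man whose study-clinic record matches but who refills outside the linked area is linked.
- Fallback matching: it is described for missing, mismatched or duplicate folder numbers, not for a valid match with no recent activity.
- Relocation criterion: it covers planned moves to another region, not a change of clinic within the metro.
- Subdistrict matching: it can capture a man who moves to another clinic in the same subdistrict, but not one who goes further. Clinic-level matching captures neither.
- Laboratory data: these could show care elsewhere, but no rule ties them to retention.

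**The case against.** **A stronger reading is that the protocol counts men who resume ART elsewhere as failures.** It does not say so. The outcome definition does not restrict the visit to the study clinic, and the coding of transfers may stand in a statistical analysis plan, which was not available. Failure is the natural reading of a two-category outcome with this data source, but it is an inference. Subdistrict matching, if chosen, would also reduce the problem.

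**A reader might infer that coaches steer men to or from the study clinic, so that the error must differ by arm.** No text or figure supports this. Study staff acting as Linkage Officers encourage all listed men to return before randomisation, a pull common to both arms. A differential error is possible because only one arm has coaches; its direction and size are unknown.

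**A reader might also infer that physical files will be checked more often in one arm.** The protocol makes no link between coach knowledge and file retrieval. What stands is only that no trigger for the check is fixed.

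**The power loss may be counted twice.** The 40-60% range comes partly from clinic data. If it describes recorded retention, unseen care is already out of the control figure. This stands, with one limit: it removes the loss fully only if the 10 points are also meant as recorded retention. If only the 50% is recorded and the 10 points are true, m = 10% gives 50% vs 50 + 10 × 0.90 = 59%, and power at 400 per arm is about 73%. The protocol does not say which is meant.

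**Laboratory data are imperfect evidence.** A test at month 6 says nothing about supply at month 12, and coaching could itself change testing. This stands, and it limits what the fix can claim.

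**Conclusion.** The point holds as a gap in how the primary outcome is ascertained. The source and its reach are set in the protocol, the level is left open between two unequal options, and none of the named safeguards reliably detects ART resumed outside the linked area. Whether the resulting error is large, and whether it differs by arm, cannot be established from the protocol.

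Under assumed misses differing by 5 percentage points of the truly retained, a true 10-point effect is read as 6.5 to 12 points and a null as 2.5 points in either direction. These figures show that bias is possible, not that it is likely. An equal miss attenuates the difference without creating an effect, and its cost in power is not established. The change is worth making because it is cheap and bears on the primary comparison.

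**What to change.** 1. Fix one TIER.Net linkage level for both arms: at least subdistrict, wider if obtainable.
2. State how a visit and refill at another facility are classified.
3. For every man without a qualifying TIER.Net record, apply the same search, blind to arm, of the physical files and of the NHLS data already requested. TIER.Net status alone should trigger it.
4. Pre-specify a sensitivity analysis of the primary comparison that reclassifies as retained those men with an HIV-monitoring test at another facility in a stated window close to month 12, not across the whole of months 6-12. Report the number reclassified by arm.

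The cost is wording in the protocol or analysis plan and some matching work. A laboratory test is weaker evidence of supply than a refill record, so the laboratory-based result should remain a sensitivity analysis and not replace the primary definition.
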